## Methodology

Given the challenges in obtaining a sufficient sample of patients with acute coronary syndrome (ACS) to prospectively compare fentanyl to morphine, the study will focus on chest pain patients in the emergency department. These patients typically have blood drawn initially and again two hours later to check for elevation and changes in troponin levels, a cardiac muscle protein detectable when cardiac muscle is being injured. These blood draws will be supplemented by evaluating platelet aggregation at the 0 and 2-hour marks.

There are many measures and techniques in evaluation of platelet function. Light Transmission Aggregometry (LTA) looks at changes in light transmittance through serum as platelets aggregate, leading to increased light transmission as more platelets aggregate. Aspirin interferes with arachidonic acid mediated aggregation because of its effects upon COX-1 conversion of arachidonic acid to thromboxane A2. Arachidonic acid is therefore the best trigger to use to evaluate aspirin's effect upon platelets, as opposed to epinephrine, ADP, or several others used to evaluate the stronger anti-platelet oral and IV agents that act in different places in the platelet activation cascade (8).

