#### **Research Design**

Patients who have 0 and 2 hour troponins ordered will have their chart reviewed by the research coordinator for candidacy in the study (see below for inclusion/exclusion). If the patient meets study entry criteria then platelet aggregation studies using arachidonic acid will be added on to the 0 and 2 hour lab draw.

The study will compare the 0 and 2-hour platelet aggregation scores of patients receiving aspirin who are undergoing two sets of troponin tests. The first group will consist of patients not receiving any narcotics, the second group will include those receiving morphine, and the third group will include those receiving fentanyl. The treating clinician will determine the appropriate pain treatment plan for each patient.

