### Sample/Participants

The research coordinator will perform chart review on Emergency Department patients presenting with chest discomfort. If there are 2 sets of troponins ordered and no exclusion criteria then the research coordinator will approach the patient for consent.

Inclusion criteria: Adult Emergency Department patients undergoing 0 and 2 hour troponin testing who have been administered aspirin within 30 minutes of the initial blood draw. Initially all patients undergoing this testing will be candidates for the study. We will attempt to enroll 80 patients in the each of the 3 arms. Determination of which (if either) narcotic is administered will be up to the clinician. As we reach the enrollment goals our research coordinator will discuss with the clinicians the expected pain plan to tailor enrollment of patients in the treatment arms that are still needed

Exclusion criteria: Patients not expected to get a 2 hour troponin; patients already on aspirin, clopidogrel, or stronger anti-coagulants; patients who arrived via EMS given it can be difficult to find the run reports to determine whether patient received fentanyl in the pre-hospital period; pregnant patients; patients on chronic narcotics; patients already once enrolled in this study, inability to provide consent in English

With regards to at risk populations, Economically Disadvantaged, Nursing home residents, prisoners, homeless patients are all commonly encountered in the ED. However, the request of 1 or 2 blue top tubes (totaling about a teaspoon of blood) is not an onerous ask. Since narcotic use (or non-use) will be wholly up to the provider and not impacted by this study we see no problems with including them.

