#### Instrumentation-Data collection

If consent is given to obtain the labs then the research coordinator will extract basic demographic information into a spreadsheet (name, MRN, age, sex, race, ethnicity), as well as the results of the labs including the CBC data already obtained (hemoglobin and platelet count). We will record the patients' creatinine to also help describe our population. Finally the platelet aggregation data that we are studying will be recorded, as well as confirmation with the patient that they are not on anti-platelet medicines such as aspirin, clopidogrel (Plavix), aspirin-dipyridamole (Aggrenox), prasugrel (Effient), ticagrelor (Brilinta). We will record time and dosing of aspirin administration, time and dosing of narcotic medicines (morphine, fentanyl, dilaudid).

This spreadsheet would be maintained on SH-Lakeland servers in a location only accessible to the research coordinator and PI.

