# **Data Analysis Procedure**

In the PACIFY trial, at 2 hours, patients receiving fentanyl had a PRU value of 113 +/- 94 on the platelet aggregation study (light aggregometry using ADP) after receiving Brilinta (ticagrelor), versus 71 +/- 66 in those not receiving fentanyl. With an alpha of 0.05 and beta of 0.8, 57 patients would be required to demonstrate statistical significance if there is a similar magnitude of effect. In the PERSEUS trial at 2 hours, patients receiving fentanyl had a PRU value of 173 +/-90 after also receiving Brilinta (ticagrelor), versus 210 +/- 76 in those receiving morphine and Brilinta (ticagrelor). 74 patients would be required to show statistical significance in direct comparison of morphine vs fentanyl. The aim is to enroll 80 patients in each arm (no narcotic, morphine, and fentanyl).

Two-tailed T-testing will be used to look for differences in the 2 hour platelet reactivity response rates between those receiving morphine versus those not receiving narcotics and between those receiving fentanyl and those not receiving narcotics.

If the data is sent to the Spectrum Health SASS team for analysis MRN's will be converted to a study ID so that the actual MRN will not be sent out.

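### Non-aspirin NSAIDs act on the pathway that the assay reads, yet the plan neither screens for recent use nor records use in the emergency department

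*Combined protocol and SAP*

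**What the plan says.** Methodology justifies the assay by mechanism: "Aspirin interferes with arachidonic acid mediated aggregation because of its effects upon COX-1 conversion of arachidonic acid to thromboxane A2". Arachidonic acid is therefore preferred to the other triggers.

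The drug-related exclusions in Sample/Participants are "patients already on aspirin, clopidogrel, or stronger anti-coagulants" and "patients on chronic narcotics". The same section excludes everyone who arrives by ambulance, because fentanyl given before arrival can be hard to trace.

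Instrumentation-Data collection provides for "confirmation with the patient that they are not on anti-platelet medicines such as aspirin, clopidogrel (Plavix), aspirin-dipyridamole (Aggrenox), prasugrel (Effient), ticagrelor (Brilinta"). For drugs given in the ED it says: "We will record time and dosing of aspirin administration, time and dosing of narcotic medicines (morphine, fentanyl, dilaudid"). NSAIDs are not mentioned anywhere in the document.

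Under Research Design, "The treating clinician will determine the appropriate pain treatment plan for each patient", and the control arm is defined only by the absence of one drug class: "The first group will consist of patients not receiving any narcotics". Data Analysis Procedure then states: "Two-tailed T-testing will be used to look for differences in the 2 hour platelet reactivity response rates", comparing each narcotic arm with the no-narcotic arm. No covariate is named.

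**The concern.** The assay was chosen because it is specific to the step that aspirin blocks. Non-aspirin NSAIDs also inhibit COX-1. That is general pharmacology and is not stated in the document. A low 2-hour value therefore cannot be credited to aspirin alone unless other drugs acting at that step are kept out or at least recorded.

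As written, a walk-in patient who took an NSAID at home that morning is eligible. So is a patient given an NSAID in the ED, who is assigned to an arm by narcotic use alone, with the NSAID not captured. The protocol already treats prior aspirin use and untraceable pre-hospital fentanyl as grounds for exclusion, and an unrecorded NSAID is a problem of the same kind.

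Three consequences are possible:

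- **Commoner in the no-narcotic arm:** that arm's 2-hour aggregation falls for a reason other than aspirin, and the narcotics appear to impair aspirin when they may not. Both planned comparisons share this control arm.
- **Commoner in a narcotic arm:** that arm's aggregation falls, and a real narcotic effect is hidden.
- **Equally common:** patients whose platelets are already inhibited can show little narcotic effect, and the difference is diluted.

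**Working it through.** **Inputs from Data Analysis Procedure.** Two-sided alpha 0.05; power 0.80 (the plan's beta of 0.8 read as power); 80 patients per arm; fentanyl 113 (SD 94) versus no fentanyl 71 (SD 66), taken from the cited ticagrelor trial.

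**The plan's own figure.** Difference 113 − 71 = 42. Mean SD (94 + 66)/2 = 80. Then n per arm = 2 × (1.960 + 0.842)² × 80²/42² ≈ 57, which matches the stated 57. The root-mean-square SD of 81.2 gives 59. The design effect is 42/80 = 0.525 SD.

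**Assumptions not in the documents.** An NSAID lowers an exposed patient's 2-hour value by s = 0.5, 1.0 or 1.5 SD. The share exposed in one arm exceeds that in the comparison arm by f = 10, 20 or 30 percentage points, with the comparison arm taken as unexposed. A value of s this large requires appreciable aggregation still present after aspirin.

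**Unequal exposure, no true narcotic effect.** The spurious difference is b = f × s. The exposed arm is a mixture with variance 1 + f(1 − f)s², so SE = √[(2 + f(1 − f)s²)/80]. The rejection probability is P(Z > 1.96 − b/SE) + P(Z < −1.96 − b/SE).

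For f = 20%:
- s = 0.5: b = 0.10, SE = √(2.04/80) = 0.160, b/SE = 0.63, rejection 9.6%.
- s = 1.0: b = 0.20, SE = √(2.16/80) = 0.164, b/SE = 1.22, rejection 23%.
- s = 1.5: b = 0.30, SE = √(2.36/80) = 0.172, b/SE = 1.75, rejection 42%.

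The full grid of type I error is:

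| Excess exposure f | s = 0.5 SD | s = 1.0 SD | s = 1.5 SD |
|---|---|---|---|
| 10 points | 6% | 9% | 15% |
| 20 points | 10% | 23% | 42% |
| 30 points | 15% | 44% | 73% |

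The rates are the same whichever arm carries the excess; only the sign of the false difference changes. As s approaches zero, every cell returns to 5%.

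**Equal exposure, true effect 0.525 SD.** If a fraction f of each arm is already inhibited and shows no narcotic effect, the mean difference is 0.525 × (1 − f). With SE = √(2/80) = 0.158 SD:

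| f | Effect (SD) | Effect/SE | Power |
|---|---|---|---|
| 0 | 0.525 | 3.32 | 91% |
| 10% | 0.473 | 2.99 | 85% |
| 20% | 0.420 | 2.66 | 76% |
| 30% | 0.368 | 2.32 | 64% |

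With the root-mean-square SD of 81.2 the same sequence is 90%, 84%, 74% and 63%.

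**The case against.** **Direction.** A reader might infer that NSAID use must concentrate in the no-narcotic arm, because an NSAID is the natural alternative to a narcotic, and so that the plan is tilted towards its own hypothesis. The documents do not support this. They give no NSAID use by arm. The literature review names nitroglycerin as the usual first drug for discomfort, so many no-narcotic patients may have responded to it or had little pain. Patients in more pain may receive an NSAID together with a narcotic, which would reverse the bias.

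**Size.** Every participant receives aspirin, which acts on the same COX-1 step. If aspirin has largely abolished arachidonic-acid aggregation by 2 hours, an added NSAID has little left to suppress and the type I error moves back towards 5%. The 0.525 SD effect also comes from a different drug and a different agonist (ticagrelor and ADP). This objection stands, and it makes the percentages illustrative only.

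**Repair at analysis.** A reader might also infer that the damage could never be undone. That goes too far. The medical record number is kept, so NSAIDs given in the ED could be retrieved later from the medication record. The 0-hour sample might reveal suppression by a drug taken at home. These safeguards are partial. Uncharted home use would stay unknown, and a 0-hour sample cannot show a drug given after it. Aspirin within 30 minutes of the first draw may come before it, which would blur the 0-hour value. The stated test uses 2-hour values only.

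**Open-ended question.** The list of anti-platelet medicines is introduced as examples, so a coordinator could ask about NSAIDs. Nothing requires it.

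**Conclusion.** The gap is real: the plan selects a COX-1 readout but has no provision for other COX-1 inhibitors in eligibility, data collection or analysis. Unequal use would bias the 2-hour comparisons, in a direction that cannot be told from the documents, and equal use would cost power. On the stated assumptions, a 20-point imbalance gives a type I error of about 10% to 42% at 80 per arm, and equal exposure of 10% to 30% takes power from about 91% to between 85% and 64%. Both ranges rest on assumed NSAID frequencies. The first also assumes enough aggregation left after aspirin for an NSAID to lower it by 0.5 to 1.5 SD; the second assumes that exposed patients show no narcotic effect. The supportable conclusion is that the plan cannot detect or account for this exposure as written, not that a false positive for the hypothesis is the likely result. It should be corrected before enrolment, when this is cheapest.

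**What to change.** - **Sample/Participants:** add recent use of a non-aspirin NSAID before arrival to the exclusions, alongside prior aspirin use. The investigators should set and justify the look-back period.
- **Instrumentation-Data collection:** add NSAIDs to the patient confirmation question. Record the name, dose and time of any NSAID given in the ED before the 2-hour draw.
- **Data Analysis Procedure:** report ED NSAID use by arm. Pre-state a sensitivity analysis that excludes, or adjusts for, patients given an NSAID before the 2-hour draw.

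Patients given an NSAID in the ED should stay in the main comparison. Removing them selects on the clinician's pain plan after presentation and could make non-randomised arms less comparable, which is why the exclusion belongs in a sensitivity analysis.

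Clinical care is unchanged. The cost is one more question, some entries from the medication record, and somewhat slower enrolment as some otherwise eligible patients are lost.

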## Setting-Where is this taking place?

Emergency Department in St Joseph.

#### Instrumentation-Data collection

If consent is given to obtain the labs then the research coordinator will extract basic demographic information into a spreadsheet (name, MRN, age, sex, race, ethnicity), as well as the results of the labs including the CBC data already obtained (hemoglobin and platelet count). We will record the patients' creatinine to also help describe our population. Finally the platelet aggregation data that we are studying will be recorded, as well as confirmation with the patient that they are not on anti-platelet medicines such as aspirin, clopidogrel (Plavix), aspirin-dipyridamole (Aggrenox), prasugrel (Effient), ticagrelor (Brilinta). We will record time and dosing of aspirin administration, time and dosing of narcotic medicines (morphine, fentanyl, dilaudid).

This spreadsheet would be maintained on SH-Lakeland servers in a location only accessible to the research coordinator and PI.

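### Neither blood-draw time is a listed study variable and the 2-hour sample has no tolerance, so the planned dataset cannot show or adjust for unequal aspirin-to-sample time between arms

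*Combined protocol and SAP*

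**What the plan says.** All references are to the combined protocol and SAP.

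- **Origin of the sample.** Under Research Design, "platelet aggregation studies using arachidonic acid will be added on to the 0 and 2 hour lab draw". There is no separate study draw.
- **Nominal timing.** Methodology describes usual practice: "These patients typically have blood drawn initially and again two hours later". It adds: "These blood draws will be supplemented by evaluating platelet aggregation at the 0 and 2-hour marks". No section gives a plus-or-minus range or a rule for an early or late second draw.
- **Entry.** Sample/Participants requires patients "who have been administered aspirin within 30 minutes of the initial blood draw", without saying before or after. The only criterion touching the second draw excludes "Patients not expected to get a 2 hour troponin", which concerns what is expected and not what happened.
- **Recorded data.** Instrumentation-Data collection lists demographics, laboratory results ("as well as the results of the labs including the CBC data already obtained (hemoglobin and platelet count"), creatinine and the aggregation data. On timing it says: "We will record time and dosing of aspirin administration, time and dosing of narcotic medicines (morphine, fentanyl, dilaudid". Blood collection times are not in the list.
- **Analysis.** Data Analysis Procedure uses two-tailed t-tests to "look for differences in the 2 hour platelet reactivity response rates", each narcotic arm against no narcotic. Nothing in the analysis refers to the actual time of sampling.

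**The concern.** The literature review rests the hypothesis on slowed absorption of oral drugs. It reports one ticagrelor trial in which fentanyl and morphine did not differ at 2 hours but did at 4, and another in which fentanyl delayed the peak concentration. Those results are for ticagrelor and not aspirin, but they are the evidence the plan relies on, and they imply that the answer can depend on when blood is taken.

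The arms are not randomised, and late enrolment is steered towards arms that still need patients. Equal sampling time across arms is therefore not assured. If narcotic patients were sampled sooner after aspirin than the others, less of the aspirin effect would have developed, and the gap would look like a narcotic effect. If they were sampled later, a real effect would be partly hidden. The planned dataset would let nobody see which, if either, had happened.

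**Working it through.** The plan states no figure on this point, so there is none to reproduce. The check is a comparison of what is needed with what is recorded, followed by an illustration of scale.

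**1. Needed against listed**

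| Purpose | Times needed | Listed |
|---|---|---|
| Audit the 30-minute aspirin rule | aspirin, first draw | aspirin only |
| Confirm the sample is near 2 hours | first draw, second draw | neither |
| Time from aspirin to endpoint | aspirin, second draw | aspirin only |

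Each purpose fails for want of a collection time.

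**2. Spread of aspirin-to-sample time**

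If the entry rule allows aspirin 30 minutes either side of the first draw, and the second draw is exactly at 120 minutes, the interval runs from 120 − 30 = 90 to 120 + 30 = 150 minutes. If a second draw were 60 minutes late (assumed; the documents give no figure), the upper end would be 150 + 60 = 210 minutes.

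**3. Illustrative bias**

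Inputs from Data Analysis Procedure: 2-hour means of 113 and 71, SDs of 94 and 66, alpha 0.05, and 80 per arm.

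- Planning difference: 113 − 71 = 42.
- Pooled SD: √[(94² + 66²)/2] = 81.2.
- Planning effect: 42/81.2 = 0.517 SD.

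Inputs assumed, because the documents give neither: aggregation changes by 0.2 to 1.0 SD per hour near 2 hours, and mean aspirin-to-sample time differs by 15 minutes between two arms.

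Bias = slope × minutes/60:

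- Low: 0.2 × 15/60 = 0.05 SD, and 0.05/0.517 = 10% of the planning effect.
- High: 1.0 × 15/60 = 0.25 SD, and 0.25/0.517 = 48%.

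**4. False-positive risk with no true effect**

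For a two-sample t-test with n = 80 per arm, the noncentrality is bias/√(2/80) = bias/0.158. The two-sided rejection probability at 0.05, on 158 degrees of freedom, is:

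| Bias (SD) | Noncentrality | P(p < 0.05) |
|---|---|---|
| 0 | 0 | 5% |
| 0.05 | 0.32 | 6.1% |
| 0.10 | 0.63 | 9.6% |
| 0.25 | 1.58 | 34.9% |

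The result runs from negligible to serious, and the documents do not say where in that range the study would fall. Lateness that is equal on average across arms adds noise but not this bias.

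**The case against.** The best defence is that this is an unlisted field and not lost information. The study spreadsheet holds the medical record number, and draw times are probably in the laboratory record, so they could be added even after enrolment. That stands. A reader might infer that unequal timing could never be detected or corrected, and the documents do not support that. The limitation lies in the dataset as planned. It would bind most on outside analysts, who would receive study IDs in place of record numbers if the data are sent to them.

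A reader might also infer that the aspirin rule goes unchecked. It does not follow: the coordinator reviews the chart for entry criteria, and applying the rule means comparing aspirin time with draw time then. What is missing is a retained field for later audit. One could argue that laboratory results carry timestamps, but the text does not say so, while it does name drug times.

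A third tempting inference is that samples at 3 or 4 hours will be counted as 2-hour values. The plan has a nominal target and no rule either way, and nothing in it shows that such draws occur.

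Finally, the bias requires timing to differ between arms, and no section documents that it does. This also stands, and is why the figures above are illustrative only.

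**Conclusion.** The point holds as a gap in planned data and analysis. Followed as written, the plan produces a dataset that cannot audit the 30-minute aspirin rule, and cannot show or adjust for differences between non-randomised arms in time from aspirin to sample. It matters because the plan's own rationale depends on timing.

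The size of any bias is unknown. The range of 0.05 to 0.25 SD, with a false-positive risk of about 6% to 35%, rests wholly on the assumed slope and the assumed 15-minute difference. It should not be read as a forecast. The change is worth making because it is cheap and lets the study check an assumption it now makes silently.

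**What to change.** 1. **Instrumentation-Data collection:** add the actual collection times of both tubes, taken from the laboratory record.
2. **Data Analysis Procedure:** report aspirin-to-second-draw time by arm. Compare arms on all samples by regression of the 2-hour value on arm, adjusting for actual aspirin-to-second-draw time.
3. **Sensitivity analysis only:** repeat the comparison in samples near 2 hours, with the limits fixed before analysis.

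Restriction should not be the primary analysis, for two reasons. Draw time is settled after treatment, so dropping patients on it could introduce selection if timing differs by arm. And a window set from the first draw does not control time since aspirin: with aspirin up to 30 minutes either side, even 120 ± 15 minutes allows 105 − 30 = 75 to 135 + 30 = 165 minutes.

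The cost is two extra data fields and slightly more analysis work. No sample is lost from the primary comparison, and the clinical troponin schedule does not change. The adjustment deals with timing only; it does not remove other differences that arise because clinicians choose the treatment.

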#### **Ethical Considerations**

There are not significant risks to this study. Two blue-top tubes of blood will be required for this study. One is already drawn and generally discarded as part of the initial rainbow of blood that's drawn. 2.7ml of blood is used to fill a blue top tube, a trivial amount. Because these labs are not used clinically, we will seek grant funding to cover these expenses.

Because this study does not pose risks we make no plans for injury compensation. This blood test is approved for research purposes only and is not used for clinical decision making so we are not concerned about incidental findings with regard to potential outlier values.

The aim of this study is to provide better understanding of commonly used medicines' potential for unintended consequences.

